Healthy Hydration Pilot in Elementary Schools

NCT06132763

05/07/2025

1. STUDY DESIGN AND METHODS. Our team recognizes the broader context that influences student hydration behavior. As such, the proposed research involves multiple components aligning with levels of the social-ecological framework to advance water equity. All schools in will have hydration stations and be operating under their model hydration policy in the 2022-23 school year. We will randomly select a pair of matched elementary schools for study inclusion. One school will serve as the Intervention school and the other as the Control. To test study aims, we will conduct a 2 (Intervention and Control) x 2 (baseline and post) cluster pilot RCT, with students nested within schools. Both schools will receive water bottles and Hydration Tip sheets. In the Intervention school, we will collaborate with student ambassadors and our Community Advisory Board (CAB) to develop hydration marketing materials. We will then pilot a 12-week intervention that includes a student-developed marketing campaign plus positive reinforcement of water bottle use in school. Teachers will receive state standards of learning-aligned lessons related to hydration. Assessments of hydration station usage will be conducted at baseline, weekly throughout the intervention, and 12-weeks (post). Beverage selection and water bottle use at lunch will be assessed at baseline, monthly throughout the intervention, and post. School personnel and 4th and 5th grade students will complete online surveys via REDCap at baseline and post. The primary aim is to determine intervention feasibility, evidenced by the ability to recruit and retain student ambassadors, implement the intervention components as planned, and ratings of school personnel satisfaction. Secondary outcomes of interest are 1) % of students with water bottles at lunch, 2) hydration station usage, and 3) sugar-sweetened beverage (SSB) selection at lunch. We will also test our protocols for assessing body mass index (BMI) and dental caries status with a subset of 3rd grade students. Although we do not anticipate change on these measures in this short duration, these will inform methods applied in a larger trial. To acknowledge the district's time and involvement in this study, each participating school will select an incentive valued up to \$500 that is related to an identified school need (e.g., kitchen, recess, or PE equipment).

1.1 Target Population and Setting. The respective school district serves >26,000 students within 25 elementary schools (22 Title I and thus eligible for this study). Students identify as Black (56%), white (21%), Latinx (19%), multiracial (3%), and Asian (2%). The majority (>90%) of students participate in the NSLP and all students receive free meals. For the current study, all Title I elementary schools will first be categorized based on race (%Black) and ethnicity (%Hispanic); two matched schools will be randomly selected and assigned to either Intervention or Control group (methods successfully applied in our prior work in this district). Potentially eligible schools have a mean enrollment of 400 students (range 145-854); we anticipate obtaining lunchroom observations from >80% of students on each rating day, for a projected sample of ~320 student observations per day in each school. Numbers will change based on the population of the selected schools. A subset of 3rd graders who have active parent consent and student assent will complete biomedical assessments.

1.2. Student Ambassadors. We will work with a local non-profit that has successful health-related programming in the schools and the school district to solicit student ambassador nominations. Both student self- and teacher nominations will be accepted. Teachers will describe ambassador roles and responsibilities, which include determining incentives, developing marketing materials and assisting the teacher ambassador with recording hydration station usage from the device, and other intervention-related tasks as relevant. Interested students will complete an interest form, signed by their parent/guardian. Teachers will select 2-3 ambassadors. In these ways, this study will build capacity and partner with students, teachers, and the CAB to enhance study relevance. To maintain study rigor, we will train students and teacher liaisons on study procedures. Ambassadors will receive compensation for this work.

1.3. Marketing Design. In the Intervention school, student ambassadors and a graphic design consultant will attend 5 meetings to develop healthy hydration promotional materials. Meetings will be guided by Appreciative Inquiry (AI) an asset-based approach to engage participants in

self-determined change that utilizes questions and dialogue to help them focus on what's working and lead to collectively developing and implementing strategies for improvement. We will apply SOAR (Strengths, Opportunities, Aspirations, Results) to marketing design. This strategic framework is based on AI principles, focuses on strengths, and includes the voices of relevant stakeholders to identify strengths, build creativity, and determine meaningful results. Ambassadors will be provided with the overall framework regarding multiple levels that influence behaviors and asked to develop messaging (words + images) to change student hydration behaviors and create a school culture that promotes healthy hydration. The final design will be selected via consensus by ambassadors, our CAB, and the investigative team. Each ambassador will be offered a gift valued at \$20/meeting for this work. These marketing materials will then be piloted within a hydration intervention in their school.

1.4. Consent Procedures. Parents/caregivers will be informed of the study via notification letters sent home by the schools, with a form to return if they wish to opt their child out of the study. Active parental consent / student assent will be obtained for 3rd graders to participate in biomedical assessments.

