1.5. Hydration Intervention. (Intervention school)

1.5.1. Hydration Kick-Off. In January 2023, the study team, in collaboration with teachers and community organizations, will host a kick-off event at the Intervention school. All pre-K through 5th grade students and teachers will receive clear refillable water bottles with carabiners (so students can attach the water bottle to their backpack, a lesson learned in our prior work), a Hydration Tip sheet, and verbal and written guidance to bring their water bottle to school daily for use at the hydration station. Students will select a decal for their water bottle and their name will be written on the bottle, a strategy to increase ownership and help if it is misplaced.

Hydration Tip Sheets and intervention information will be sent home to parents via established district parent communication strategies (in English and Spanish). Water bottles will stay at school with cleaning materials and instructions provided for each classroom.

1.5.2. Hydration Intervention. Students will be informed at Kick-off that they could receive prizes if they use their water bottle in school. We will conduct a 12-week intervention that includes: 1) a marketing campaign with student-developed materials, 2) use of incentives (determined by student ambassadors) to positively reinforce water bottle use, 3) hydration trivia, 4) hydration lessons. Marketing materials will be placed strategically in high traffic areas including hallways, school entries/exits, the lunchroom, and on floor decals and walls near hydration stations. A **Hydration Headquarters** will be set up in the school displaying a "water meter" illustrating the increasing number of water bottle refills from their school's hydration station each week (colored in weekly by student ambassadors). This CAB-generated strategy is designed to create group cohesion towards a common healthy goal and enhance student motivation. Study personnel positively reinforce water or water bottles observed in the lunchroom 1 day/week throughout the 12 week intervention. Teachers receive classroom water procedure signs with space to personalize details regarding when students can fill, store, and clean their water bottles. Laminated hydration tips will be posted in each classroom. Teachers will receive hydration lessons by subject matter and grade that align with SOL's.

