Healthy Hydration Pilot in Elementary Schools

NCT06132763

05/07/2025

D. POWER/ANALYSIS PLAN. Students, the unit of analysis, are nested within schools. Thus, we have a cluster RCT with 2 clusters (intervention and control school). To detect a 10% mean difference in water bottle usage between groups, with a common SD of 15, an unadjusted sample size of 17/group would be needed. Adjustments to this sample size were made using a variance inflation factor (based on the assumption of an ICC of .03) to accommodate homogeneity within the clusters. Using this assumption, 2 clusters of average size of 200 is sufficient to detect the hypothesized difference at $\alpha=.05$ (two-sided) and a desired power of 80%. Thus, our proposed sample will be more than adequate to evaluate study aims. Contingency tables and frequency distributions will be evaluated and descriptive and inferential statistical analysis applied. Differences between schools in % of students with water bottles, hydration station counts (per student), % of students with SSBs at lunch, and beverage intake (BEV-Q; SSB, water, milk) will be evaluated using chi-square analysis. Difference between baseline and post values on these study outcomes will indicate an intervention effect, with one-way ANOVA conducted to test group differences. We will also graphically examine monthly trends in hydration station usage by school. Paired t-tests will examine differences in these outcomes by school. We will also examine interrater reliabilities (Kappas) among dental assessors and report baseline and post body mass index (BMI, BMIz, BMI percentile) and dental caries status (ICDAS criteria), as well as any observed differences by school over time (although none are expected in this study duration) to inform methods applied in a future trial. Descriptive statistics will be applied to examine trial feasibility (e.g., recruitment, retention, satisfaction, and implementation). Triangulating all data sources will be the basis for deriving final conclusions and recommendations for our future intervention.

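### The two schools are matched on %Black and %Hispanic but not on enrolment, which is known, runs from 145 to 854, and can bear on change after baseline

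*Protocol*

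**What the plan says.** Protocol section 1.1 takes its pool from a district with "25 elementary schools (22 Title I and thus eligible for this study". The rule for forming pairs is that "all Title I elementary schools will first be categorized based on race (%Black) and ethnicity (%Hispanic"; after that, "two matched schools will be randomly selected and assigned to either Intervention or Control group". No other matching factor is named.

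The next sentence of 1.1 reports the spread in size: "Potentially eligible schools have a mean enrollment of 400 students (range 145-854". From the mean it projects "lunchroom observations from >80% of students on each rating day, for a projected sample of ~320 student observations per day in each school". It then adds "Numbers will change based on the population of the selected schools", without giving a permitted difference between the two schools.

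SAP section D describes two clusters, one per arm, and states that "2 clusters of average size of 200 is sufficient to detect the hypothesized difference". It analyses station counts per student.

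Several delivery elements do not scale with enrolment. Section 1.2 has teachers choose 2-3 ambassadors. Section 1.5.2 has study personnel reinforce water bottle use in the lunchroom on one day a week, and displays the number of "water bottle refills from their school's hydration station each week". Neither document says how many stations each school has.

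**The concern.** With many schools per arm, randomisation would tend to even out enrolment. With one school per arm it cannot, so matching is the only design tool that makes the two schools alike. The plan uses that tool for two characteristics and leaves out a third that the investigators already hold and that varies widely.

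Size can plausibly affect this trial's results in two ways.

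- **Station access.** Unless the number of stations rises with enrolment, pupils in the larger school share each station with more others. If use grows after bottles are handed out, which happens in both schools, the school with fewer stations per pupil may reach a limit sooner.
- **Delivery.** A fixed weekly visit and a fixed number of ambassadors reach a smaller share of pupils in a larger intervention school.

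Both act on change after baseline, which the SAP reads as the intervention effect. A size gap could therefore raise or lower the apparent effect, and nothing in the data from two schools could separate it out.

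**Working it through.** **Inputs from the documents.** Enrolment mean 400, range 145-854; 22 eligible schools; 80% of pupils observed (all Protocol 1.1). Average cluster size 200, ICC 0.03, difference 10, SD 15, two-sided alpha 0.05 (SAP D).

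**The plan's own figures.** The projection reproduces: 0.80 × 400 = 320 observations per school per day. The SAP's unadjusted 17 per group does not: 2 × (15 × (1.96 + 0.842)/10)² = 35.3, so 36 per group. That is a separate matter and is not relied on here.

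**Step 1: the largest possible gap.** 854/145 = 5.89. This needs the smallest and largest schools to share a racial/ethnic category, and the documents give no school-level data on that.

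**Step 2: how often a sizeable gap would arise.** The documents give no SD or shape for enrolment, so these are assumed: a beta distribution scaled to 145-854 with mean 400, SD of 120, 150 or 180, and size unrelated to category. The scaled mean is m = (400 − 145)/(854 − 145) = 0.360. With v = (SD/709)² and k = m(1 − m)/v − 1, the shape parameters are mk and (1 − m)k. Simulated pairs give:

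| Assumed SD | Shapes | P(ratio > 1.25) | P(ratio > 1.5) | P(ratio > 2) |
|---|---|---|---|---|
| 120 | 2.53, 4.51 | 0.62 | 0.36 | 0.12 |
| 150 | 1.49, 2.65 | 0.70 | 0.48 | 0.23 |
| 180 | 0.92, 1.65 | 0.75 | 0.56 | 0.33 |

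A ratio above 4 has probability of at most 3%.

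**Step 3: what such a gap means for fixed delivery.** If the intervention school has 1.5 times the pupils of another school, the same visit and ambassadors give 1/1.5 = 67% of the contact per pupil; at 2 times, 50%.

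**Step 4: whether size matters for power.** Effective n per school = m/(1 + (m − 1) × 0.03), where m is now the cluster size. SE = 15 × √(1/n₁ + 1/n₂), and power = Φ(10/SE − 1.96). The ICC enters only as variance inflation, with no penalty for having two clusters.

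| Pupils analysed per school | Effective n | Nominal power |
|---|---|---|
| 200 / 200 | 28.7 / 28.7 | 71.4% |
| 320 / 320 | 30.3 / 30.3 | 73.7% |
| 145 / 854 | 27.3 / 32.1 | 72.6% |
| 116 / 683 (80% of 145 / 854) | 26.1 / 31.8 | 71.4% |
| 116 / 116 | 26.1 / 26.1 | about 67% |

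The most unequal pair does no worse than 200/200, because effective n cannot exceed 1/0.03 = 33.3 at any size.

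**Step 5: whether enough pairs remain.** Suppose the 22 schools are split evenly into 4 to 9 categories (an assumed number; an uneven split gives more pairs). Four categories of 6, 6, 5 and 5 hold 15 + 15 + 10 + 10 = 50 pairs. Nine categories, four of 3 and five of 2, hold 12 + 5 = 17 pairs. From step 2, 25-38% of pairs lie within a ratio of 1.25. That leaves about 12 to 19 pairs with four categories and about 4 to 6 with nine.

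**The case against.** The case against has real weight, and most of its parts stand.

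- **Baseline.** The design is baseline/post, and the SAP takes change as the effect. A stable difference linked to size is present at baseline and largely drops out. This stands; only change that depends on size remains, and the documents do not allow it to be quantified.
- **Scaling.** Outcomes are percentages or per-student counts. This removes the trivial effect of headcount, but not a limit on access or diluted contact.
- **Purpose.** The primary aim is feasibility, summarised descriptively. This limits the harm, but station use and bottle use are still compared between schools.
- **Delivery.** Ambassadors and reinforcement belong to the intervention school alone, so dilution depends on that school's own size. Matching does not set that size; it ensures a control school of similar scale, and reporting enrolment lets the reader judge the dose.

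A reader might infer three stronger points, none of which the documents support.

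- **That a near six-fold gap is to be expected.** It is a theoretical maximum and remote under the assumptions used here.
- **That any school yielding fewer than 200 observations breaches the plan.** The SAP's 200 is an average across two clusters that it calls sufficient, not a per-school minimum. Under the same assumptions the pair's mean enrolment falls below 200 in only 0.2-4% of draws.
- **That unequal size costs appreciable power, or that access per student can be calculated.** Power barely moves, and no station counts or capacities are given.

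**Conclusion.** The point holds as one of comparability. Section 1.1 leaves out of the matching a known school characteristic that can plausibly affect change after baseline, in a design where matching is the only protection. A gap of more than 1.5-fold would arise in about 36-56% of random pairs and more than 2-fold in 12-33%. Those figures rest on the assumed beta shape, the SD of 120-180, and independence of size and racial/ethnic category; actual school-level enrolments would replace them. The resulting bias has no calculable size from the documents. There is no power argument and no ground for a minimum enrolment. Matching on size would make the comparison cleaner, but school and intervention would remain confounded in every other respect.

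**What to change.** In section 1.1, add enrolment as a matching variable within each %Black/%Hispanic category. For example, form only pairs whose enrolments differ by no more than about 25%, and compare students per hydration station where that is known. Then select one pair at random and randomise within it. The 25% is a working tolerance, to be checked against the actual list of 22 schools. Report both schools' enrolment and students per station with the results.

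The cost is a sentence or two in 1.1, using enrolment figures already available, and fewer candidate pairs; step 5 suggests enough would remain.

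The documents are dated May 2025 and describe a January 2023 kick-off. If the schools have already been chosen, the reporting still applies, station results should be read in that light, and the matching rule carries over to the larger trial.

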1.5. Hydration Intervention. (Intervention school)

1.5.1. Hydration Kick-Off. In January 2023, the study team, in collaboration with teachers and community organizations, will host a kick-off event at the Intervention school. All pre-K through 5th grade students and teachers will receive clear refillable water bottles with carabiners (so students can attach the water bottle to their backpack, a lesson learned in our prior work), a Hydration Tip sheet, and verbal and written guidance to bring their water bottle to school daily for use at the hydration station. Students will select a decal for their water bottle and their name will be written on the bottle, a strategy to increase ownership and help if it is misplaced.

Hydration Tip Sheets and intervention information will be sent home to parents via established district parent communication strategies (in English and Spanish). Water bottles will stay at school with cleaning materials and instructions provided for each classroom.

1.5.2. Hydration Intervention. Students will be informed at Kick-off that they could receive prizes if they use their water bottle in school. We will conduct a 12-week intervention that includes: 1) a marketing campaign with student-developed materials, 2) use of incentives (determined by student ambassadors) to positively reinforce water bottle use, 3) hydration trivia, 4) hydration lessons. Marketing materials will be placed strategically in high traffic areas including hallways, school entries/exits, the lunchroom, and on floor decals and walls near hydration stations. A **Hydration Headquarters** will be set up in the school displaying a "water meter" illustrating the increasing number of water bottle refills from their school's hydration station each week (colored in weekly by student ambassadors). This CAB-generated strategy is designed to create group cohesion towards a common healthy goal and enhance student motivation. Study personnel positively reinforce water or water bottles observed in the lunchroom 1 day/week throughout the 12 week intervention. Teachers receive classroom water procedure signs with space to personalize details regarding when students can fill, store, and clean their water bottles. Laminated hydration tips will be posted in each classroom. Teachers will receive hydration lessons by subject matter and grade that align with SOL's.

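### Does the lack of a rule keeping lunchroom ratings off the weekly reward day distort the bottle-use result in the Intervention school?

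*Protocol*

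**What the plan says.** The reward visit belongs to the Intervention school's programme (Protocol, section 1.5.2): "Study personnel positively reinforce water or water bottles observed in the lunchroom 1 day/week throughout the 12 week intervention". The weekday is not given. Students hear at the kick-off that using their bottle may earn a prize, but no prize is tied to a particular day. Water without a bottle is reinforced too, and bottles are kept at school.

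The rating schedule is in Protocol section 1: "Beverage selection and water bottle use at lunch will be assessed at baseline, monthly throughout the intervention, and post". No rating weekday is given, and neither is the number of rating days at post. Post is placed at 12 weeks for hydration station usage; the post lunch rating is not dated separately. Section 1.1 expects more than four-fifths of pupils to be seen whenever ratings are made, and states the volume of data that results: "for a projected sample of ~320 student observations per day in each school".

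On the standing of the outcome, section 1 says "The primary aim is to determine intervention feasibility" and then "Secondary outcomes of interest are 1) % of students with water bottles at lunch". SAP section D treats the baseline-to-post difference as the sign of an intervention effect, and draws its conclusions from all data sources together.

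**The concern.** The rewarded behaviour and the measured behaviour are nearly the same, in the same room and over the same weeks, and only one school has reward days. The monthly ratings must fall within the reward period. The post rating may do so as well if it follows the 12-week timing given for station usage. If study staff combined the reward visit and the rating visit for convenience, the rating could capture a reward-day peak and not typical bottle use. Baseline has no reward days and the Control school has none described, so a difference in changes would carry the peak in full. Counting more students on that day would not average it out.

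The SAP sizes the study on a 10-point difference in bottle use. A peak of several points would therefore matter to anyone reading the school contrast as an effect estimate.

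**Working it through.** The plan gives no figure for this point. Its one directly relevant number reproduces: mean enrolment 400 x 80% = 320 observations per day per school (Protocol, section 1.1).

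**Inputs from the documents.** One reward day a week for 12 weeks, Intervention school only (section 1.5.2). About 320 observations per rating day (section 1.1). Target difference 10 points, SD 15, ICC 0.03, average cluster size 200 (SAP section D).

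**Assumptions, not in the documents.** D = rise in bottle carrying on a reward day, in points. p = chance that the post rating falls on a reward day. Five school days a week. A single post rating day.

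**Step 1: error about the weekly mean.** The weekly mean includes one-fifth of the lift, 0.2 x D. A reward-day rating is too high by D - 0.2 x D = 0.8 x D. A rating on any other day is too low by 0.2 x D.

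**Step 2: expected bias.** p x 0.8 x D - (1 - p) x 0.2 x D = (p - 0.2) x D.

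**Step 3: root mean squared error (RMSE).** MSE = p x 0.64 x D² + (1 - p) x 0.04 x D² = (0.04 + 0.6p) x D².

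| Scheduling | p | Bias | RMSE | Bias for D = 5, 10, 15 | RMSE for D = 5, 10, 15 |
|---|---|---|---|---|---|
| Ratings kept off reward days | 0 | -0.2 x D | 0.20 x D | -1, -2, -3 | 1, 2, 3 |
| Days set independently | 0.2 | 0 | 0.40 x D | 0, 0, 0 | 2, 4, 6 |
| Half coincide | 0.5 | +0.3 x D | 0.58 x D | 1.5, 3, 4.5 | 2.9, 5.8, 8.7 |
| Always coincide | 1 | +0.8 x D | 0.80 x D | 4, 8, 12 | 4, 8, 12 |

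So on one rating day a separation rule has the smallest RMSE, but it exchanges scatter without bias for a fixed understatement.

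**Step 4: more than one post day.** With k independently chosen days the RMSE is 0.4 x D / √k. At k = 4 this is 0.2 x D, equal to the rule. Beyond that it is smaller, whereas the rule's -0.2 x D does not shrink with more days.

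**Step 5: sampling error for scale.** Treating students as independent, one school's percentage has an SE of at most √(0.25/320) = 2.8 points. A two-school contrast at post has √2 x 2.8 = 4.0, and a difference in changes 2 x 2.8 = 5.6. With D = 5 and independent days, the rule would move the RMSE from 2 points to 1.

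**Step 6: a different target.** If the target is use on non-reward days, the shift is D x the share of post ratings on reward days. On the SAP's inputs the design effect is 1 + 199 x 0.03 = 6.97, the effective n is 200/6.97 = 28.7, and the SE is 15 x √(2/28.7) = 3.96 points. With no true effect on non-reward days, the nominal 5% test would reject as follows.

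| D | Share on reward days | Shift (points) | Rejection rate |
|---|---|---|---|
| 5 | 20% | 1.0 | 6% |
| 5 | 50% | 2.5 | 10% |
| 5 | 100% | 5.0 | 24% |
| 10 | 20% | 2.0 | 8% |
| 10 | 50% | 5.0 | 24% |
| 10 | 100% | 10.0 | 71% |

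Steps 1 and 6 give different answers for the same schedule: zero expected bias in one, +1.0 point in the other, for D = 5 and a 20% overlap. The difference lies entirely in which target is chosen, and the documents do not settle that.

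**The case for a change.** The best case for acting is that the omission can be verified, that any distortion would sit in one arm, and that prevention costs one sentence. The incentive component itself presumes that prizes alter bottle use, so some lift is plausible. With bottles kept at school, taking one to lunch could respond to a same-day cue. Sharing a visit between rewarding and rating would be convenient, so p could well exceed 0.2. In the worst case, full overlap with D = 10, the rating is 8 points above the weekly mean, or 10 points above a non-reward day, which is the whole of the SAP's target difference.

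The gap in the text stands, as does the conditional arithmetic. What does not follow is that the plan as written gives a wrong result. The lift, the overlap and the single post day are all supposed. Reinforcing water without a bottle could make the lift for bottles small, and a post rating after the last reward visit would have no overlap at all. Nor is separation certain to remove the lift: if the cue is study staff in the lunchroom and the raters are also study staff, which the documents do not say, an off-day rating visit could prompt the same reaction.

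**Conclusion.** No change to the plan is called for. The documents leave the rating weekday, the date of the post lunch rating and the number of post days to the study team, and they show neither overlap nor a reward-day lift. The figures of 4, 8 and 12 points require an assumed D of 5, 10 or 15, a single post day and certain coincidence. Under independent scheduling the expected bias about the weekly mean is zero.

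Separation is a debatable trade-off, not a correction. Reinforcement is part of the intervention, so excluding its days understates average use by 0.2 x D, while including them at random adds scatter that several rating days would reduce. Either choice is defensible for a secondary outcome in a pilot whose primary aim is feasibility. With one school per arm, school and intervention are confounded in any case. Hydration station counts are taken weekly from the device and do not depend on the lunch rating day, and the monthly lunch ratings give further points.

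Timing points the same way. The kick-off was planned for January 2023 (Protocol, section 1.5.1) and the documents are dated 05/07/2025, so a 12-week programme run to schedule would be long finished and a scheduling rule could not affect it. What remains is descriptive: saying which rating days were reward days, and reading the bottle-use contrast accordingly. Analysts can supply that when reporting, without an amendment.
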